among young people. Preliminary evaluation data collected among an initial cohort of roughly 27,000 users has shown high levels of engagement in the program and high rates of abstinence among responders. Roughly ¾ of users set a quit date, with the most common quit date being the day of enrollment. Interactive keywords were used by 45.5% of teens and 38.4% of YA. Response rates to follow-up assessment questions were 36.9% at 14 days and 21.0% at 90 days. At 14 days, 60.8% of respondents indicated they had reduced or stopped using e-cigarettes altogether. At 90 days, 7-day point prevalence abstinence (ppa) was 25% and 30-day ppa was 16%. The high volume of enrollment in a short period of time, high levels of engagement with the program, and e-cigarette reduction and cessation results demonstrate that young people are interested in quitting vaping and can be engaged in an easily accessible, anonymous digital platform.

We recently completed an evaluation of This is Quitting with 2,588 young adults aged 18-24. Under an intention-to-treat analysis with missingness coded as vaping, abstinence rates were 24.1% among participants assigned to the intervention (This is Quitting) and 18.6% among participants in the assessment only control arm, a statistically significant difference (Odds Ratio=1.39, 95% CI 1.15-1.68, p< 0.001). [10]

Building on previous research, the primary aim of the current study is to conduct a comparative effectiveness trial to evaluate the effectiveness of *This is Quitting* in promoting abstinence from e-cigarettes among adolescents aged 13-17. This study is a 2-arm randomized controlled trial conducted among young users aged 13-17 recruited through online channels. Participants will be randomized to *This is Quitting* or an assessment-only control condition and followed for 7 months to roughly correspond to 6-months post-treatment. The secondary aim is to examine potential mediators of program effectiveness, including treatment engagement and changes in self-efficacy and perceived social support for quitting.

We will also include a waitlist control arm to evaluate the influence of assessment reactivity and retention incentives given relatively high quit rates among assessment-only control participants in the previous YA trial and the dearth of data on adolescent vaping cessation. This arm was not included in sample size calculations.

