The scientific, clinical, and public health communities are desperate for proven, evidence-based cessation resources to address the vaping epidemic among young people. We are uniquely positioned to address this urgent need given our extensive experience in conducting large-scale, rigorous research trials of digital tobacco cessation interventions and our expertise in working with young people. We plan to rapidly disseminate study results to benefit other researchers/service providers and use these results to further enhance the program.

METHODS

Subjects

We will randomize 1800 e-cigarette users aged 13-17 years old who are interested in quitting in the next 30 days to the two main intervention arms (900/arm). We will aim to randomize 450 to the waitlist control arm. Other eligibility criteria include past 30-day e-cigarette use and US residence. To fully enroll in the study, individuals must text a study-specific phone number and respond to the system-generated message.

Recruitment and Enrollment

Potential participants will respond to online ads on various social media platforms (Facebook, Instagram, etc.) if they are current e-cigarette users who are interested in quitting and willing to participate in a research study. Clicking on the ad will lead them to a webpage that provides details about what participation in the study entails and describes incentives for participation. Those who are interested will complete an eligibility screener followed by informed consent and a baseline assessment. Those who complete the baseline will be randomized into one of three arms (see below for additional details) and instructed to text a specific keyword corresponding to their treatment assignment to the same phone number. Only those who respond to the first message from the text message program within 24 hours will be fully enrolled into the study. This requirement will be made explicit.

Randomization

Randomization occurs after completion of the online enrollment process (completed baseline survey). A computer algorithm that is part of the survey software will automate random allocation.

Interventions

This is Quitting: Participants will be enrolled to receive messages from This is Quitting as described above.

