Participants will be 1,800 e-cigarette users aged 13-17 who respond to online advertising about a research study and who complete enrollment into a text message program based on random allocation. Study enrollment is conducted entirely online and is fully automated. Randomization occurs after participants have provided informed consent, passed the decisional capacity check, and completed the baseline survey. Study enrollment will not be considered complete until the participant responds to the initial system-generated text message.

We will be recruiting adolescent participants under the age of 18 and we are requesting a waiver of parental consent. This approach is based on published research with adolescents engaging in high-risk behavior as well as the American Psychological Association Resolution on Support for the Expansion of Mature Minors' Ability to Participant in Research.³² Parents are often unaware of their adolescent's use of ecigarettes and many adolescents hide their e-cigarette use from their parents for fear of punishment and disapproval, making parental consent a significant barrier to studying e-cigarette use and treatment among teens. As noted in the APA resolution, requiring parental consent in adolescent research may lead to biased samples, causing researchers to overestimate or underestimate the scope of health problems in at-risk populations and leading to findings that is not generalizable to the population of adolescent vapers who want to quit vaping. Research supports that children as young as 14 years old can provide valid informed consent similarly to adults when information is presented at developmentally appropriate levels and the

consent process is conducted under minimal stress. Adolescents that meet study eligibility criteria will be provided information about the study at a 5th grade reading level and required to complete a series of questions showing decisional capacity before they continue with study enrollment.

Sources of Materials

Sources of research material include the following: 1) screening data, 2) text message utilization data, and 3) baseline and follow-up assessments. The baseline assessment will be conducted online with the survey hosted on a secure server. Mixed-mode follow-up (online, phone, text message) will be employed. Phone surveys will be conducted by research staff blind to treatment condition.

Materials Access

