Step 1 (Study information): Potential participants who click on an online ad for e-cigarette users who are interested in quitting and willing to participate in a research study will be directed to a website that provide additional details about the study. This webpage will provide information on who is behind the study, what participation entails, and who may be eligible for the study. Step 2 (Eligibility screening): Individuals who are interested in participating will complete a short survey to confirm eligibility for study participation. Those who are eligible will be asked to provide contact information (e-mail address to send links to surveys and mobile number for text message sign up). Step 3 (E-mail confirmation): An email message is sent to the participant with a distinct URL (Web address) containing the baseline survey and instructions to complete the survey within 24 hours to complete study enrollment. This process ensures that enrolled participants have a valid email address where they can receive study-related correspondence. Step 4 (Informed consent): When the participant clicks on the URL in the email, it will open up an online baseline survey. On the first page of the baseline survey, the Informed Consent text will be provided, including a) each study condition; b) financial incentives for participating; c) the process of randomization and the equal chance of being assigned to one of three treatment conditions; d) protection of confidentiality and the right to withdraw at any time; and e) expectations regarding follow-up data collection, including compensation for time required to complete follow-up assessments (regardless of e-cigarette use status). Users will be required to select "Yes, I would like to continue" as active affirmation that they are providing consent for study participation. Contact information for the study and the Institutional Review Board where IRB approval has been obtained will be included in the Informed Consent form. All information about the study will be written at a 5th grade reading level to ensure adequate comprehension. Step 5 (Decisional capacity confirmation): After reading the informed consent, they will be asked to complete an assessment of decisional capacity and understanding of the informed consent by answering the following 7 questions:

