What is the purpose of this study?; Do you have to be in this study?; Can you tell me what will happen if you agree to take part in this study?; How might this study not help you or even hurt you?; How might this study help you?; What would you do if you wanted to leave the study?; What will happen if you decide not to be in the study? Correct answers will be required for all 7 questions in order for the potential participant to move onto the Baseline assessment. Step 6 (Baseline assessment): Users who respond correctly to the decisional capacity questions will move onto the baseline assessment. Step 7 (Randomization): Randomization will only occur after an eligible study participant has completed the online enrollment process (confirmed eligibility, indicated informed consent, passed decisional capacity confirmation, and completed baseline survey). Step 8 (Text message sign-up): Users will be randomized at the conclusion of the baseline assessment and provided with a keyword to text based on their assignment. Users must text their assigned keyword to the provided phone number and reply to the welcome text message to confirm text message enrollment and finalize their study enrollment. Those who are willing to provide additional contact methods will be asked to add their social media handle for private messaging at this step (optional).

POTENTIAL BENEFITS OF THE PROPOSED RESEARCH TO HUMAN SUBJECTS AND OTHERS

Subjects may benefit from participation in this research in several ways. By participating in an e-cigarette cessation treatment program, subjects may increase the likelihood that they will attempt to quit e-cigarette use and be successful. Alternatively, participants will gain a greater understanding of their e-cigarette use behavior that may help them to quit successfully in the future. Finally, although this is not a direct benefit, all participants will be involved in a project to evaluate innovative treatments for e-cigarette cessation that may ultimately produce an enormous public health impact. We believe the substantial potential benefits significantly outweigh the minimal potential risks to research participants.

Payment for participation

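### The consent description of an equal chance of three conditions cannot produce the planned arm sizes of 900, 900 and 450, and the Randomization section does not say which holds

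*Combined protocol and SAP*

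**What the plan says.** Under Adequacy of Protection Against Risks, Step 4 (Informed consent) lists what the consent text will cover, including "the process of randomization and the equal chance of being assigned to one of three treatment conditions". This is the only allocation probability in the document.

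Methods, Subjects, gives the numbers. It assigns 1,800 adolescents "to the two main intervention arms (900/arm"), and adds: "We will aim to randomize 450 to the waitlist control arm".

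The three arms are filled in one step. Recruitment and Enrollment says "Those who complete the baseline will be randomized into one of three arms", and Step 8 (Text message sign-up) says "Users will be randomized at the conclusion of the baseline assessment and provided with a keyword to text based on their assignment".

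On the mechanism, the Randomization section says only that randomization follows the baseline survey and that "A computer algorithm that is part of the survey software will automate random allocation". It gives no ratio, weights, blocks, arm cap or closing rule. The three items in the Summary of Changes do not concern allocation.

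Two further statements bear on the numbers. The background says of the waitlist: "This arm was not included in sample size calculations". Human Subjects Involvement, Characteristics, and Design says "Participants will be 1,800 e-cigarette users aged 13-17 who respond to online advertising about a research study", a count that leaves the waitlist out.

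**The concern.** The described chance and the planned sizes belong to the same randomization, so each fixes the other. An equal three-way chance leads to equal arms, but the plan has a waitlist half the size of each main arm. If the sizes are right, the chance described to participants is wrong. If the described chance is right, the sizes cannot all be met.

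What is at stake is the accuracy of a consent element that the protocol itself lists, for participants aged 13-17 enrolled under a requested waiver of parental consent. The arm decides whether the study delivers the program to a participant. It also decides the maximum payment, because text assessments are paid only in the two main arms. In addition, with no ratio or closing rule stated, a reader cannot tell whether the waitlist and the assessment-only controls were recruited over the same period. That matters for any comparison between them.

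**Working it through.** **Inputs.** Main arms 900 and 900; waitlist 450, stated as an aim (Subjects). One randomization into three arms at the end of baseline (Recruitment and Enrollment; Step 8). Described chance 1/3 for each condition (Step 4). The document gives no overall total; the targets sum to 900 + 900 + 450 = 2,250.

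**Formula.** Expected arm size = number randomized × probability of that arm.

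**Do the planned sizes follow from the described chance?**

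| Scheme | Program | Assessment-only | Waitlist | Total |
|---|---|---|---|---|
| Planned | 900 | 900 | 450 | 2,250 |
| 1:1:1, total fixed at 2,250 | 750 | 750 | 750 | 2,250 |
| 1:1:1, main arms fixed at 900 | 900 | 900 | 900 | 2,700 |
| 1:1:1, waitlist fixed at 450 | 450 | 450 | 450 | 1,350 |

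No version of equal allocation reproduces the plan. Chance imbalance does not explain the gap: with a true 1/3 chance, the exact binomial probability of 450 or fewer waitlist assignments among 2,250 is about 8 × 10⁻⁴⁵.

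**Which schemes do reproduce it?**

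1. *Constant 2:2:1.* 2,250 × 2/5 = 900, 900, and 2,250 × 1/5 = 450. The chances are 40%, 40% and 20%. Described minus actual: program 33.3 − 40 = −6.7 points; waitlist 33.3 − 20 = +13.3 points.

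2. *1:1:1 until the waitlist reaches 450, then 1:1.* The first stage takes an expected 3 × 450 = 1,350 people, 450 per arm. The remaining 2,250 − 1,350 = 900 split 450 and 450. The main arms end at 450 + 450 = 900 each. The description is true for the first 1,350 (60%). The last 900 (40%) have no chance of the waitlist and a 1/2 chance of each main arm.

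In both schemes the chance of the program is at least 1/3 for everyone.

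**Maximum payment by arm** (Payment for participation). Surveys: 2 × (20 + 10) = USD 60. Main arms: 60 + 7 × 5 = USD 95, which matches the stated maximum. Waitlist, with no paid text assessments: USD 60. The chance of an arm with the USD 95 maximum is 2/3 = 66.7% as described, against 4/5 = 80% under 2:2:1.

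**Count in the human subjects section.** 2,250 − 1,800 = 450, which is the waitlist target.

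**The case against.** The strongest reply is that the waitlist number is soft and the mismatch has little effect. The 450 is an aim, and the arm was outside the sample size calculations, so it may have been meant to be filled and then closed. Both main arms are treated alike under every reading. Any error in the described chance of the program runs in the participant's favor.

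Much of this stands. The fill-then-close scheme gives the planned totals as exactly as 2:2:1 does, so a reader who infers that the ratio is 2:2:1 goes further than the documents allow. The smaller waitlist target also has a plausible reason. But an aim of 450 does not stretch to 750 or 900, a reason for a smaller target does not set a ratio, and no closing rule is written. Fill-then-close would still make the description untrue for the last 900 people. Loss at the text-reply step does not explain the gap either, because the Subjects section gives its figures as numbers randomized.

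A reader might also infer that the arm decides whether a participant can get the program. The documents do not support that. The background describes open sign-up by text message, with more than 350,000 young people enrolled by July 2021, and nothing bars control participants from joining that way. The payment difference is pay for answering extra assessments, and Step 4 lists the conditions and incentives as separate consent content.

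Nor can one conclude that participants read an inaccurate form. The consent form is not among the documents reviewed, so the point concerns only the protocol's description of it.

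**Conclusion.** Wrong as written; minor. The equal chance in Step 4 and the sizes in Subjects cannot both hold, and the Randomization section does not settle which does.

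The size depends on the scheme used. Under a constant 2:2:1 ratio, the described chance is 6.7 points too low for the program and 13.3 points too high for the waitlist. Under fill-then-close, it is wrong for about 900 of 2,250 participants. If allocation is truly equal, the waitlist is 750 or about 900, depending on whether the total or the main arms are held fixed, against an aim of 450. These figures assume a single randomization into three arms and the stated targets.

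Two stronger readings fail. A reader might infer bias in the primary result, but the program and assessment-only arms have the same chance as each other under every scheme considered, so that comparison is not biased. A reader might also infer that participants were promised better odds than they got. Under both schemes that deliver the planned sizes, nobody's odds of the program fall below those described. No loss of power is claimed.

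**What to change.** Check the allocation setting in the survey software. State in the Randomization section the ratio actually used and any cap or closing rule for the waitlist. Then make the Step 4 description and the planned arm sizes agree with it.

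If recruitment is over, which the approval dates of 2021-2022 and reference access dates of April 2024 suggest but do not prove, report the ratio used and the wording participants saw. If the ratio changed during recruitment, restrict any comparison of waitlist with assessment-only to participants randomized over the same period.

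As a minor alignment, make the total in Human Subjects Involvement, Characteristics, and Design include the waitlist: 2,250 if the stated targets stand.

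The cost is one software check plus protocol and consent wording, or reporting only if recruitment has closed. No extra participants are needed under either scheme that gives 900/900/450. Only keeping equal allocation with 900 per main arm would add people: 2,700 − 2,250 = 450.

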Assessment-only control: After an initial enrollment message, participants will be contacted monthly to assess e-cigarette use. At the end of the study, participants will receive information about how to sign up for This is Quitting if they are interested.

Waitlist control: After an initial enrollment message, participants will only be contacted at 1 and 7 months to complete the follow-up assessments; there will be no other contact via text message. At the end of the study, participants will receive information about how to sign up for This is Quitting if they are interested.

Potential Problems and Solutions

Loss to follow-up is the primary concern in trials involving digital interventions, especially ones that employ an assessment only or minimal contact controls. For the treatment and assessment only control arms, we expect at least 75% follow-up at 1-month and 65% at 7-months based on our previous and ongoing digital mobile-based evaluations. If follow-up rates are lower than expected early in the trial, we will consider shortening the 7-month follow-up to gather only abstinence outcomes.

To maximize follow up rates we will:

- 1) provide clear information about the study at the outset, including expectations for follow-up;
- 2) reimburse participants up to \$30 per follow-up assessment;
- 3) collect interim abstinence assessments via text ("Retention Messages": \$5 incentive for each response) for intervention and assessment-only control arms;
- 4) send reminders about follow-up surveys via email and text messages;
- 5) conduct phone follow-ups for those unreachable by email and text messages;
- 6) contact participants via social media private messaging function (if permission given); and,
- 7) emphasize the importance of survey completion regardless of abstinence status.

Conducting research online involving incentives carries the potential for fraud and participant deception as there are often no direct interactions with the participants.¹¹ To prevent fraudulent enrollments and participation from bots, we will utilize the following features on the Qualtrics survey platform:

- 1) Prevent multiple submission: Enabling this option allows Qualtrics to place a cookie on the browser the first time someone takes the survey. The user will be flagged as duplicate if they come back to take the survey from the same browser and device without having cleared their cookies.

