Missing Data. Missing data will be handled in two ways. First, we will conduct an intent-to-treat (ITT) analysis in which participants who have been lost to follow up are assumed to be treatment failures (i.e., vaping). This analysis will be conducted because ITT analyses are common in the smoking cessation literature, despite simulations demonstrating that the approach is neither conservative nor anti-conservative but rather biased in favor of whichever condition contains less missingness. Second, we will supplement the ITT analyses with an analysis that uses a multiple imputation (MI) procedure to minimize bias in estimates and standard errors, under the assumption that outcomes are not missing at random (NMAR) but rather more likely to be missing for treatment failures (i.e., vaping) than treatment successes (i.e. abstinence). Since the magnitude of actual response bias is unknown, we will conduct a sensitivity analysis to evaluate the treatment effect on outcomes under a range of magnitudes, from equal odds of missing (OR=1) to five times more likely to be missing (OR=5).

Mediator Analysis. Our conceptual model is that treatment increases the odds of abstinence by increasing perceived social support and perceived self-efficacy for quitting. Those two constructs will be measured at baseline, 1-month and 7-months post-treatment. Change in those constructs from baseline will be evaluated with separate mediation analyses as presented in Figure 1. Specifically, we hypothesize that the effect of treatment on abstinence will be mediated by perceived social support and perceived self-efficacy, such that: (1) a significant effect A is found associating X with Z; (2) a significant effect B is found associating Z with Y; (3) a significant effect C is found associating X with Y; and (4) the effect of C is significantly attenuated when A and B are simultaneously included in the model.

PROTECTION OF HUMAN SUBJECTS

Human Subjects Involvement, Characteristics, and Design

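### The optional social media handle, a supplementary retention route, is requested only after allocation, so who can be reached by it may depend on the arm; asking before randomization is a cheap improvement.

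*Combined protocol and SAP*

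**What the plan says.** The enrolment steps are under Adequacy of Protection Against Risks. Step 2 (Eligibility screening) takes two contact details from everyone eligible: "e-mail address to send links to surveys and mobile number for text message sign up". In Step 4, "the Informed Consent text will be provided, including a) each study condition; b) financial incentives for participating". Step 7 is randomization. Step 8 (Text message sign-up) then reads: "Users will be randomized at the conclusion of the baseline assessment and provided with a keyword to text based on their assignment". After describing the keyword text and the reply to the welcome message, Step 8 says that willing participants are "asked to add their social media handle for private messaging at this step (optional". No earlier request for a handle appears.

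Methods, Recruitment and Enrollment, confirms that the keyword is specific to the arm: participants are "instructed to text a specific keyword corresponding to their treatment assignment to the same phone number".

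Potential Problems and Solutions names loss to follow-up as the main concern. For the intervention and assessment-only arms it states "we expect at least 75% follow-up at 1-month and 65% at 7-months". Its sixth of seven retention measures is to "contact participants via social media private messaging function (if permission given".

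Under Missing Data in the Data Analysis Plan, the first analysis treats those lost to follow-up as vaping, and the plan describes this approach as "biased in favor of whichever condition contains less missingness".

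**The concern.** A contact detail collected before allocation cannot be affected by the arm. One collected afterwards can. By Step 8 the participant has read a description of every condition and holds a keyword tied to one of them. Someone pleased with the assignment may be readier to give one more contact route than someone who is not, or the reverse.

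The handle is then available to the study team when follow-up is pursued. If it brings in more outcomes in one arm, coding the missing as vaping turns the extra reach into extra apparent abstinence there. What is at stake is a small, avoidable contribution to differential missingness in the primary outcome, self-reported 30-day abstinence at 7 months. The plan does not mention comparing handle provision or contact mode by arm.

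**Working it through.** The point concerns the order of procedures, so the plan has no figure of its own to reproduce. The arithmetic below only bounds the size.

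**Order of events.** E-mail and mobile number (Step 2), consent (Step 4), capacity check (Step 5), baseline survey (Step 6), randomization (Step 7), keyword and handle (Step 8). Whether the handle field comes before or after the welcome-message reply is not stated. On either reading it follows allocation.

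**Inputs from the documents.** Follow-up of 65% at 7 months, hence m = 1 − 0.65 = 0.35 otherwise missing; 900 per main arm; abstinence with missing coded as vaping of 24.1% and 18.6% in the earlier young adult trial (introduction), used for illustration only.

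**Assumptions, not in the documents.** Uptake gap between arms u = 5 to 20 points; share of otherwise missing handle-givers recovered r = 10% to 50%; the 65% expectation also applied to the earlier trial's rates, to obtain abstinence among those reached.

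**Step 1: follow-up gap = u × r × m.**
- Low: 0.05 × 0.10 × 0.35 = 0.00175, or 0.2 points.
- Middle: 0.10 × 0.25 × 0.35 = 0.00875, or 0.9 points.
- High: 0.20 × 0.50 × 0.35 = 0.035, or 3.5 points.

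**Step 2: spurious abstinence difference = gap × q**, with no true effect and q the abstinence among those reached, equal in both arms. With q = 0.186/0.65 = 0.286:
- Low: 0.175 × 0.286 = 0.05 points (odds ratio 1.003).
- Middle: 0.875 × 0.286 = 0.25 points (odds ratio 1.017).
- High: 3.5 × 0.286 = 1.0 points (odds ratio 1.067).

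With q = 0.241/0.65 = 0.371, the high end is 3.5 × 0.371 = 1.3 points.

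**Step 3: allow for recovered participants being likelier to vape.** Step 2 gives them the average responder's abstinence. The plan's own sensitivity range lets vapers be up to five times likelier to be missing. Dividing the odds of abstinence, q/(1 − q), by that factor gives the rate q′ among those recovered. From q = 0.286:
- Factor 2: q′ = 0.167, difference 0.03 to 0.58 points.
- Factor 5: q′ = 0.074, difference 0.01 to 0.26 points.

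**Step 4: error rates** (two-proportion normal approximation, two-sided 5%, 900 per arm). For follow-up gaps of 0.8 to 2.4 points and q from 0.286 to 0.371:

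| Factor | Spurious difference (points) | Type I error |
|---|---|---|
| 1 | 0.2 to 0.9 | 5.2% to 7.2% |
| 2 | 0.13 to 0.55 | 5.1% to 5.8% |
| 5 | 0.06 to 0.25 | 5.0% to 5.2% |

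In the other direction, if 24.1% versus 18.6% were the true rates, power would be 81.3%. Lower follow-up in the program arm, with the gap split evenly around 65%, changes it as follows:
- 0.8-point gap, factor 1: 77%.
- 2-point gap, factor 1: 71%.
- 2-point gap, factor 2: 75%.
- 2-point gap, factor 5: 79%.

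**The case against.** The channel is supplementary. Measures and Sources of Materials list the follow-up modes without social media, and text message is named as the last means of obtaining abstinence data from non-responders. E-mail and mobile number are held for everyone before allocation. This stands, and it is the main reason the effect is likely to be small.

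Nothing in the documents shows that uptake differs by arm, or that the keyword's wording reveals the arm. This also stands. The point is a possibility created by the order of steps, not an observed imbalance.

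The plan already discloses the bias and adds multiple imputation under non-random missingness. That is partial mitigation: the range varies missingness by outcome, and the text does not say whether it may differ by arm.

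Larger arm differences exist by design, notably contact intensity and the post-allocation 24-hour reply rule. That is fair as a matter of priority, but it is no reason to keep an avoidable one.

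Asking at sign-up also limits the identifiers held on adolescents who never finish enrolling. This has some weight, though the field would stay optional and such handles can be deleted.

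A reader might infer that follow-up will differ by arm, or that the trial faces a type I error near 7% or a fall in power from 81% to 71%. The documents do not support this. Those figures need a gap near the top of an assumed range and recovered participants who abstain at the average responder rate.

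**Conclusion.** The point holds as a small, cheap improvement. A retention contact is requested after allocation when it could be requested before, and the first analysis is sensitive to unequal reach. Under assumed follow-up gaps of 0.2 to 3.5 points, the spurious abstinence difference is from under 0.1 to about 1 point. It is probably below half a point, because other routes reach everyone and hard-to-reach participants are likely to abstain less than average. The direction cannot be predicted. All of this rests on assumed uptake gaps and channel yield, and the true gap could be zero. The documents do not support calling the primary comparison biased on this ground.

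**What to change.** Move the optional handle question into the baseline survey (Step 6), after consent and before the randomizer runs. The expected uptake gap between arms is then zero. The cost is reordering one survey screen. A small downside is that handles are also collected from some adolescents who never complete text sign-up; these can be deleted.

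If enrolment has already begun, tabulate handle provision and mode of outcome capture by arm, and repeat the primary analysis treating outcomes obtained only after social media contact as missing. This needs the contact route behind each outcome to have been recorded.
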